- i. **Aim 1:** Feasibility and Acceptance of NEW Tx in the Nonrandomized Trial (N=6). *Hypothesis 1a:* A preliminary study of whether NEW Tx will be feasible with regards to recruitment, retention, blinded assessments, and therapist adherence to NEW Tx⁴³. *Hypothesis 1b:* Participants will report high satisfaction with the treatment (CSQ-8) and acceptability (NEW Tx Scale) over the study duration (i.e., 20-weeks) in a nonrandomized trial ($n = 6$).
- ii. **Aim 2:** Feasibility and Acceptance of NEW Tx and its Evaluation in the Randomized Pilot Trial ($n = 40$). *Hypothesis 2a:* A pilot study of whether NEW Tx will be feasible with regards to recruitment, randomization, retention, blinded assessments, and therapist adherence to NEW Tx⁴³. *Hypothesis 2b:* Participants will report high expectations for the treatment (CEQ) and high satisfaction and acceptability with the treatment (CSQ-8; Post-Tx Questionnaire; NEW Tx Scale) in a 20-week nonrandomized trial ($n = 6$).

B. Exploratory Aims

- i. **Aim 3a:** Reducing Medical Burden in the Randomized Pilot Trial. Pilot test ($n = 40$) the efficacy of NEW Tx in improving medical burden using the Framingham Risk Score (FRS). *Hypothesis 3a:* Over the course of 20-weeks (18 sessions) the NEW Tx group will have a lower FRS compared to treatment as usual (TAU) in the randomized pilot trial.
- ii. **Aim 3b:** Symptoms and Functioning in the Randomized Pilot Trial. Examine the efficacy of NEW Tx in improving functioning and symptoms of BD. *Hypothesis 3b:* Over the course of 20-weeks (18 sessions) the NEW Tx group will improved functioning (LIFE-RIFT) and symptoms (YMRS, MADRS) compared to TAU in the randomized pilot trial.
- iii. **Aim 3c:** Moderator and Mediator of NEW Tx in the Randomized Pilot Trial. Investigate a potential moderator and mediator of treatment response. *Hypothesis 3c.1:* Individuals with higher baseline BMI (>30) will moderate the between treatment effect size for medical burden (FRS) in the randomized pilot trial, such that of NEW Tx will have lower FRSs. *Hypothesis 3c.2:* Mastery of the diet (food diaries) and exercise (exercise duration from Exercise Questionnaire) modules of NEW Tx will mediate the association of NEW Tx and improvement in medical burden (FRS).

III. INTERVENTION MODULES AND OVERVIEW

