- xv. **Post-Treatment Questionnaire** is an open-ended, 3 question measure that asks participants to identify aspects of the treatment that were helpful or not helpful and that could be improved.
- xvi. **Intent to Attend⁷²** is a single item that measures participants' intent to attend the next study visit which will be used in part to inform the extent to which attrition is ignorable⁷³.
- xvii. **DXA scans** measure total body composition and fat content using low-dose x-rays.
- xviii. **University of Rhode Island Change Assessment Scale (URICA)** is a 32-item, self-administered measure that is a reliable and valid measure of motivation and intention to change at entrance to treatment.
- xix. **Metabolic Cart Assessment**—Metabolic Cart Assessment—A metabolic cart is an electronic medical tool that is used to measure basal metabolic rate and can be used by medical professionals to determine someone's overall health condition. This test indirectly measures how much energy a person's body uses at rest by measuring the amount of oxygen a person consumes versus the amount of carbon dioxide a person expends.

Table 1. Schedule of Assessments for the NEW Tx and TAU groups

Weeks	0	1	2	3	4	5	6	7	8	9	10	11	12	13	14	16	18	20	32
	Pre										Mid							Post/ET	Follow-Up
MINI	x																		
Medical Hx	x																		
Psychiatric Hx	x																		
Demographics	x																		
PAR-Q	x																		
CGI-BP	x										x							x	x
Blood Draw**	x										x							x	x
Vitals	x									x							x	x	
DXA scan	x																x		
CMF	x									x							x	x	
MADRS	x									x							x	x	
YMRS	x									x							x	x	
LIFE-RIFT	x									x							x	x	
NEW Tx Scale																	x	x	
CEQ	x																		
CSQ-8																	x	x	
URICA	x																x	x	
Met Cart	x																x		
Post-Tx Questionnaire																	x	x	

EQ	x	x	x	x	x	x	x	x	x	x	x	x	x	x	x	x	x	x	x	x	x
Intent-to-Attend†	x	x	x	x	x	x	x	x	x	x	x	x	x	x	x	x	x	x	x	x	
Food Diaries†	x	x ¹	x	x ¹	x	x ¹	x	x ¹													

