ET= Early Termination. Vitals = Height (at Week 0 and Week 20), weight, waist circumference, blood pressure, pulse, and Dual X-Ray Absorptiometry (i.e., body composition). ** Includes lipid profile (i.e., cholesterol, triglycerides), metabolic panel (i.e., blood urea nitrogen (BUN), creatinine (Cr), electrolytes, blood glucose level), complete blood count (CBC), and thyroid stimulating hormone (TSH). C reactive protein (CRP) and inflammatory marker panels (Human TH1/TH2 10-Plex (IFN-g, IL-1b, IL-2, IL-4, IL-5, IL-8, IL-10, IL-12p70, IL-13, TNF-a)) will be included at pre- and post-treatment visits. A urine pregnancy test will be administered at Week 0 to determine eligibility. An EKG will be completed at Week 0 for participants \geq 40-years-old, if clinically indicated.

¹As needed.

†For the TAU group, will only be collected at Weeks 0, 10, and 20

Table 2. Schedule of Assessments for the Waitlist Group (TAU participants who choose to receive NEW Tx)Weeks	21	22	23	24	25	26	27	28	29	30	31	32	33	34	35	36	37	38	39	40	52
										Mid-tx									Post-tx	Follo w-up	
CGI-BP										x									x	x	
Blood Draw**										x									x	x	
Vitals										x									x		
DXA scan																			x		
CMF										x									x	x	
MADRS										x									x	x	
YMRS										x									x	x	
LIFE-RIFT										x									x	x	
NEW Tx Scale																			x	x	
CSQ-8																			x	x	
URICA	x																		x	x	
Met Cart	x																		x		
Post-Tx Questionnaire																			x	x	
EQ	x	x	x	x	x	x	x	x	x	x	x	x	x	x	x	x	x	x	x	x	
Intent-to-Attend	x	x	x	x	x	x	x	x	x	x	x	x	x	x	x	x	x	x	x	x	
Food Diaries	x ¹																				

ET= Early Termination. Vitals = weight, waist circumference, blood pressure, pulse, and Dual X-Ray Absorptiometry (i.e., body composition). ** Includes lipid profile (i.e., cholesterol, triglycerides), metabolic panel (i.e., blood urea nitrogen (BUN), creatinine (Cr), electrolytes, blood glucose level), complete blood count (CBC), and thyroid stimulating hormone (TSH). C reactive protein (CRP) and inflammatory marker panels (Human TH1/TH2 10-Plex (IFN-g, IL-1b, IL-2, IL-4, IL-5, IL-8, IL-10, IL-12p70, IL-13, TNF-a)) will be included at pre- and post-treatment visits. A urine pregnancy test will be administered at Week 0 to determine eligibility.

¹As needed.

D. Independent Evaluator Training

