Baseline demographic and clinical characteristics will be examined by the PI in collaboration with [name]., Professor of Biostatistics. Measures of central tendency and variability will be estimated on each continuous measure; proportions estimated for categorical variables. Transformations will be used when distributional assumptions are not fulfilled for inferential tests. Dropouts and completers will be compared on baseline variables using Mann-Whitney or chi-square tests.

A. Data Management: REDCap

To ensure the quality of electronic data capture (EDC) and management, the data management team will use the REDCap EDC system. The REDCap Consortium is comprised of 135 active institutional partners and it supports two secure, web-based applications (REDCap and REDCap Survey) designed to support data capture for research studies. The REDCap application is currently in production use or development build-status for more than 2990 studies with over 9540 end-users spanning numerous research focus areas across the consortium, and the REDCap Survey application is now being adopted rapidly by consortium partners. Both REDCap and REDCap Survey provide a process for building a database or online survey, an interface for collecting data, data validation, and automated export procedures for data downloads to statistical packages (SPSS, SAS, Stata, R).

REDCap allows users to design and implement study scales to collect, store, retrieve, and manipulate data electronically. The REDCap platform for EDC that streamlines data collection and management, and the system is a study management tool used to monitor visit timing and completion in real-time, thus helping to minimize missing data. REDCap is already used at MGH for treatment studies and has proved extremely useful for conducting and managing studies. It obviates the need for data entry by staff, thus minimizing cost and human error. Furthermore, because data quality control checks can be built into the logic of the online measures, problems can be identified in real-time, thereby improving data quality and consistency.

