Research staff will enter scale and assessments responses into the REDCap electronic assessment forms. Using 128 bit RSA Secure Socket Layer (SSL) encryption, approved users will be logged-in to machines using secured browsers behind the Partners Healthcare Systems IS corporate firewall or the RIH firewall. Staff will have a unique identifying key that will link them to the electronic study forms. This unique ID will be used in addition to a randomly generated secure password that only the staff person will have. Additional confidentiality procedures are detailed in the Human Subjects section.

B. Statistical Analyses Plan for Research Aims

Each of the statistical tests below will use a two-tailed alpha-level of 0.05.

- i. **Aim 1: Feasibility in Nonrandomized Trial (Phase I).** *Hypothesis 1a:* Descriptive statistics will be used to report the number of intervention sessions attended (we expect > 80%), number of participants recruited per month, and therapist adherence to NEW Tx (average adherence score ≥ 6). *Hypothesis 1b:* Participants will report high satisfaction (total CSQ-8 score, $M > 24^{75}$) with the treatment and acceptability (total NEW Tx Scale score, $M < 25$, or at least an average score of “agree” on half of the items).
- ii. **Aim 2: Feasibility in Randomized Trial (Phase II).** *Hypothesis 2a:* Descriptive statistics will be used to report the number of intervention sessions attended (we expect > 80%), number of participants recruited per month, randomization rate (number randomized/number consented), number of assessment sessions attended (we expect > 80%), and retention (number of study completers/number randomized) (we expect > 80%, which is conservative for diet and exercise interventions for severe mental illness^{25, 76-78}) and therapist adherence to NEW Tx (average adherence score ≥ 6). *Hypothesis 2b:* Participants will report high expectations (CEQ score) for the treatment and high satisfaction and acceptability (CSQ-8, Post-Tx Questionnaire, NEW Tx Scale).

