- iii. **Aim 3: Exploratory Aims (Phase II).** *Hypotheses 3a and 3b:* Between treatment group effects sizes (and 95% CI) will be calculated. To supplement this, Mann-Whitney tests will compare treatment groups on medical burden (as measured by FRS) (*Hypothesis 3a*) and on improvement in symptoms (MADRS, YMRS) and functioning (LIFE-RIFT) (*Hypothesis 3b*) based on change from baseline. *Hypothesis 3c.1:* We will investigate baseline BMI as a potential moderator of treatment response. The focus will be on the magnitude of the effect, not on significance testing. The between treatment group effect sizes (i.e., FRS, MADRS, YMRS, LIFE-RIFT) will be compared with those who have high baseline BMI (> 30) versus low BMI (< 30). *Hypothesis 3c.2:* Mastery of the diet (Nutrition Data System score of food diaries) and exercise (weekly exercise duration from Exercise Questionnaire) modules will mediate the association of NEW Tx and improvement in medical burden (FRS). The

dependent variable will represent change in the FRS score from time of completion of respective module. The mediators will be tested separately. Differential between treatment group effect sizes for those who did and did not master the modules will provide evidence of a mediator of treatment.

C. Rate of Attrition

Some attrition (i.e., 20%) is expected and this can result in bias and reduce power, precision and generalizability⁷⁹. Consistent with the Intent to Treat principle⁸⁰, we will continue with the assessments for the study duration, even among those who fail to comply with the treatment⁸¹. As one aspect of the feasibility study, we will assess the likelihood to attrite using the “Intent to Attend” measure⁷².

D. Power Analysis

The sample sizes for the Phase I and II trials are based primarily on the fundamental aim of this project: feasibility. The N is not based on what is needed for inferential analyses as they are not a fundamental aspect of the design. Power analyses are not indicated for the proposed exploratory analyses. We acknowledge that we will not have sufficient power to detect large effects (e.g., $d = .80$).

IX. REFERENCES

1. Hennekens C. Increasing global burden of cardiovascular disease in general populations and patients with schizophrenia. *Journal of Clinical Psychiatry*. 2007;68(suppl 4):4-7.

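### The only specified dropout comparison pools the two arms and relies on low-powered significance tests, so it says little about attrition bias in NEW Tx versus TAU

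*Combined protocol and SAP*

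**What the plan says.** The opening paragraph of Section VIII (Data Analysis) states: "Dropouts and completers will be compared on baseline variables using Mann-Whitney or chi-square tests". Treatment arm is not mentioned. Nothing in VIII.B or VIII.C adds a split by arm, and retention under Aim 2 is defined over all randomized participants together.

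VIII.C (Rate of Attrition) recognises the risk: "Some attrition (i.e., 20%) is expected and this can result in bias and reduce power, precision and generalizability".

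A second source of information is planned. Section IV.C, item xvi, describes the Intent to Attend item, "which will be used in part to inform the extent to which attrition is ignorable". VIII.C returns to it: "As one aspect of the feasibility study, we will assess the likelihood to attrite". Neither place gives a model, a summary or a decision rule. The Table 1 footnote adds a difference in schedule: "For the TAU group, will only be collected at Weeks 0, 10, and 20". In NEW Tx the item is scheduled throughout treatment.

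Three provisions limit or document losses. VIII.C continues assessments in people who do not comply with treatment. Table 1 labels the Week 20 column as also serving for early termination. VII.A has reasons for early termination reported to the DSMB.

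**The concern.** A randomized comparison is biased by attrition when the people lost from one arm differ from those lost from the other. A pooled dropout-versus-completer comparison asks a different question: whether leavers in general differ from stayers. If sicker patients leave NEW Tx and healthier ones leave TAU, the two patterns offset each other in the pooled table.

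The design gives reasons why selection might differ. NEW Tx asks for 18 sessions. TAU participants who complete 20 weeks are offered NEW Tx, an incentive to stay that exists only in that arm. Substantial clinical deterioration leads to withdrawal, so any treatment effect on deterioration would change who leaves.

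At stake are the effect sizes under Hypotheses 3a and 3b, since Phase II is meant partly to estimate an effect size. The reliance on significance tests adds to the problem, because few dropouts are expected.

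**Working it through.** **Inputs.** Attrition is 20% (VIII.C) and allocation is 1:1 (IV.A). The randomized N is given as 40 in the Specific Aims and 60 in IV.A and IV.B, so both are carried. The two-sided 0.05 level is stated in VIII.B for the tests that follow it; applying it to the dropout comparison is an assumption. The documents give no power figure for this comparison, so there is none to reproduce. The SD shifts below are assumed.

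**1. Expected dropouts.** 0.20 × 40 = 8 (8 v 32). 0.20 × 60 = 12 (12 v 48).

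**2. What the pooled comparison measures.** Let D_A and D_B be the dropout-minus-completer differences in the two arms, in SD, and q the dropout fraction. Randomization gives the arms the same expected baseline mean, so completers in an arm sit at -qD.
- Between-arm gap among those remaining: |q_A·D_A - q_B·D_B|.
- Pooled difference with equal dropout: (D_A + D_B)/2.

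With equal dropout, the gap depends on the difference between D_A and D_B, while the pooled table shows their average.

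**3. Limiting case.** Four of 20 leave each arm, at +1 and -1 SD from the arm mean. Completers shift by (4 × 1)/16 = 0.25 SD in opposite directions, a gap of 0.50 SD. With 6 of 30 the shift is 6/24 = 0.25, the same. Here D = 1 + 0.25 = 1.25 SD within each arm, and the pooled difference is (1.25 - 1.25)/2 = 0.

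**4. Milder cases (q = 0.20).** D = ±0.5 gives 2 × 0.20 × 0.5 = 0.20 SD. D = ±0.8 gives 2 × 0.20 × 0.8 = 0.32 SD.

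**5. Rejection rates under opposite selection (20,000 simulated trials per case).**

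| Setting | Pooled Mann-Whitney | Each arm alone | Arm-by-dropout interaction |
|---|---|---|---|
| N=40, ±0.5 SD | 3.7% | about 11% | 23% |
| N=40, ±0.8 SD | 2.3% | about 22% | 51% |
| N=60, ±0.5 SD | 3.7% | about 16% | 33% |
| N=60, ±0.8 SD | 2.5% | about 35% | 68% |

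The pooled test rejects no more often than under no selection. With unequal dropout (6 v 2, or 9 v 3), it rejects in about 8-10% of trials at ±0.5 SD and 11-17% at ±0.8 SD. These runs gave completers in both arms a common mean, which is slightly generous to the pooled test when dropout is unequal.

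**6. Power when selection is the same in both arms.**

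| Dropouts v completers | 0.5 SD | 0.8 SD | 95% CI half-width |
|---|---|---|---|
| 8 v 32 | 21-22% | 46-47% | 1.96 × √(1/8 + 1/32) = 0.78 SD |
| 12 v 48 | 31-33% | 65-66% | 1.96 × √(1/12 + 1/48) = 0.63 SD |

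By a t-test calculation, 80% power needs a difference of about 1.14 SD or 0.92 SD.

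**7. From baseline gap to effect.** Hypotheses 3a and 3b use change from baseline. Assume equal SDs at both times, a baseline-to-Week-20 correlation r of 0.3 to 0.7 (not in the documents), and loss related only to baseline. The mean change then shifts by gap × (1 - r):
- 0.20 SD gap: 0.14 to 0.06 SD.
- 0.32 SD gap: 0.22 to 0.10 SD.
- 0.50 SD gap: 0.35 to 0.15 SD.

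**The case against.** Several stronger readings are tempting, and the documents do not support them.

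- A reader might infer that this is the only planned attrition check. It is not: Intent to Attend is meant to inform ignorability. What stands is that its analysis is unspecified and its schedule differs between arms.
- A reader might infer that 3a and 3b compare completers only. The plan does not say so. Continued assessment of non-compliers and the early-termination visit mean some dropouts may contribute outcomes. The gaps above apply in full only if every dropout lacks Week 20 data.
- A reader might infer that the pooled test can never detect opposite selection. Exact cancellation needs balanced numbers and shifts; otherwise the test keeps slight sensitivity.
- A reader might infer that a non-significant result will be taken as proof of no bias. No section says this, and VIII.C states openly that attrition can bias results. It is a risk of interpretation.

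Two further objections stand. A baseline gap does not pass one-for-one into a change score (step 7). Nor would it be sound to adjust for whichever variables turn out to differ. With 16 or 24 remaining per arm, the chance SE of a standardised difference is √(2/16) = 0.35 or √(2/24) = 0.29, so 95% ranges are about ±0.69 or ±0.57. Even a 0.5 SD gap lies within chance, and such a rule would select covariates on noise. By-arm significance tests are weak too, which argues for description with intervals.

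**Conclusion.** The point holds as a minor one. The specified comparison is pooled and test-based, and it is poorly matched to the bias that matters for NEW Tx versus TAU. Under balanced opposite selection of 0.5 to 0.8 SD, it flags a difference in about 2-4% of trials while those remaining differ at baseline by 0.20 to 0.32 SD. The 0.5 SD gap is a limiting illustration, not a forecast. With 8 to 12 dropouts, non-significance is weak evidence even when selection runs the same way in both arms.

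These sizes rest on 20% attrition, the assumed shifts, equal dropout unless stated, and dropouts having no Week 20 data. The documents do not show that opposite selection will occur. Severity is limited because 3a and 3b are exploratory aims in a pilot sized for feasibility. Retention is itself a primary feasibility outcome, however, so attrition by arm is worth reporting for that reason alone.

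**What to change.** Replace the pooled tests in Section VIII with the following:

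1. A table, by arm, of dropout numbers, reasons, and baseline values for dropouts and completers.
2. Standardised between-arm baseline differences with 95% CIs among those contributing Week 20 data.
3. A statement that p-values will not be used to judge attrition harmless.
4. One sensitivity analysis for each 3a and 3b outcome, adjusted for the baseline value of that outcome and specified now, not chosen after seeing which variables differ. Mann-Whitney takes no covariates, so this needs a separate model, for example a regression of the Week 20 value on arm and baseline.
5. A sentence saying how Intent to Attend will be summarised, restricted to Weeks 0, 10 and 20 where the arms are compared.

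The cost is some SAP wording, one table and one extra model per outcome, with no new data collection. The limit should be stated as well: baseline comparisons, pooled or by arm, cannot show dropout that depends on unobserved outcomes.

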- ii. **Phase II:** In this phase, we will pilot test the NEW Tx methods compared to TAU ($n = 60$) to further examine feasibility, to estimate an effect size, and to explore its efficacy for reducing medical burden. TAU will be the control group in the Phase II pilot study as it is the standard treatment in the Massachusetts General Hospital (MGH) Bipolar Clinic and Research Program. Participants randomized to TAU who complete the first 20 weeks of the study will have the option to receive NEW Tx. TAU participants who chose to receive NEW Tx (the waitlist group) will follow the same procedures as the NEW Tx group over an additional 20 weeks such that they will have assessments at Weeks 30, (mid-treatment), 40 (post-treatment), and 52 (follow-up) (see Table 2). For TAU, medication and dosage changes are allowed as long as the change is recommended based on the guidelines and participants remain on a mood stabilizer. Medication changes will be monitored with the Clinical Monitoring Form Medication Module. All participants will have a three-month follow-up visit during which post-treatment measures and assessments will be repeated. Participants will be recruited with the same criteria as the nonrandomized trial, but will be randomized using a 1:1 allocation ratio with a blocking strategy. The assessments will be similar to those used in Phase I. In addition to the study staff utilized in Phase I, clinicians with training in CBT and mood disorders will be added as NEW Tx therapists.

B. Participant Selection and Recruitment

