An EKG will be required for participants over the age of 40, if clinically indicated, to further minimize potential risks associated with exercising. For clinical monitoring and assessment of adverse events, a fasting blood draw will be conducted at Week 0, Week 10, and Week 20. For the waitlist group (i.e., TAU participants who choose to receive NEW Tx after 20 weeks), fasting blood draws will be conducted at Weeks 30, Week 40, and Week 52, in addition to the aforementioned draws. Drug screens will not be required; however, administration of drug screening as part of ongoing treatment is at the discretion of the treating physician at any time after consultation with the participant.

C. Diagnostic and Clinical Assessments

- i. **Extended Mini-International Neuropsychiatric Interview** (MINI⁵⁷) will be used to establish DSM-IV diagnoses including BD, substance use, and eating disorders.
- ii. **Demographics, Medical History, and Psychiatric History** forms will assess any pertinent medical or psychiatric conditions that may impact the participants' eligibility or treatment in this study.
- iii. **Montgomery Asberg Depression Rating Scale** (MADRS⁵⁸) is a 10-item clinician-rated measure of depression that assesses the presence and severity of patient's current depressive symptoms.
- iv. **Young Mania Rating Scale** (YMRS⁵⁹) is an 11-item, clinician-rated measure that assesses the presence and severity of patient's current symptoms of mania.
- v. **Clinical Global Impression-Bipolar Illness** (CGI-BP⁶⁰) is a one item illness severity score that is a widely accepted, reliable, and valid assessment of global illness in BD⁶¹. The CGI-BP is a modified version of the CGI designed specifically for use in assessing global illness severity in patients with BD. This version assigns ratings for mania, depression, overall severity, and side effects.
- vi. **Clinical Monitoring Form** (CMF) Medication Module⁶² will track medication and dosage changes and whether the subject is taking medications for blood pressure (used to calculate the FSR score).
- vii. **Food Diaries** or a self-report record of foods and calories consumed will be completed by participants between study visits as needed. Selected food diaries will be reviewed by a dietitian (as needed).

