- viii. **Exercise Questionnaire** (EQ) is a modified version of the Exercise History and Attitude Questionnaire which has been used in a wide variety of settings^{63, 64}. It is typically administered to healthy populations; thus, some items were excluded that were not likely to pertain to BD. This questionnaire assesses baseline (i.e., past) exercise history as well as ongoing exercise duration and frequency at follow-up study visits⁶⁵.
- ix. **LIFE- Range of Impaired Functioning Tool** (LIFE-RIFT^{66, 67}) assesses the extent to which medical burden has impacted current functioning.
- x. **Framingham Risk Score** (FRS) will be used to estimate medical burden as it is designed to estimate risk in adults (age > 20) to predict 10-year risk for myocardial infarction and coronary death. The FRS is calculated

based on six indices: age, gender, total cholesterol, HDL cholesterol, smoker (Y/N), systolic blood pressure, and medications to treat high blood pressure (Y/N). It is one of the most widely validated and cited clinical prediction scores, and although several modifications have been proposed, a recent review of over 1900 studies found that these studies had “flaws in their design, analyses, and reporting that cast some doubt on the reliability of the claims for improved prediction”⁶⁸. The Medical History form will collect the patient data necessary to calculate the FRS score.

- xi. **Physical Activity Readiness Questionnaire (PAR-Q⁶⁹)** is a seven-item, self-report questionnaire to screen individuals for starting an exercise program. In addition to the PAR-Q, an EKG will be required for participants over the age of 40, if clinically indicated, to further minimize potential risks associated with exercising.
- xii. **Credibility/Expectancy Questionnaire (CEQ⁷⁰)** is a 6-item, self-report questionnaire to assess patients' perceptions of and expectations for treatment before the study begins.
- xiii. **Client Satisfaction Questionnaire-8 (CSQ-8⁷¹)** is a reliable and valid self-report of participants' acceptability of treatment. This is an assessment of client/patient satisfaction with their care and perceived quality and tolerability of NEW Tx.
- xiv. **NEW Tx Scale** is a 10-item scale to assess participants' acceptability of NEW Tx. This scale also includes a comments section to solicit unstructured feedback from participants on NEW Tx.

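### The exploratory 3a/3b comparison subtracts baseline but does not adjust for it; a baseline-adjusted week-20 estimate would probably be somewhat more precise at no extra data cost

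*Combined protocol and SAP*

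**What the plan says.** Section IV.A.ii gives Phase II the purpose "to estimate an effect size, and to explore its efficacy for reducing medical burden", besides feasibility. Section II.B sets a 20-week horizon for Hypotheses 3a (FRS) and 3b (YMRS, MADRS, LIFE-RIFT). Section VIII.B.iii then plans: "Between treatment group effects sizes (and 95% CI) will be calculated. To supplement this, Mann-Whitney tests will compare treatment groups on medical burden", and likewise on symptoms and functioning, "based on change from baseline".

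No baseline covariate and no regression model is named. The change-from-baseline wording stands in the Mann-Whitney sentence. The effect-size sentence has no formula and no standardiser. That the effect sizes are on the same change scale is the natural reading, not a stated rule.

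Section VIII.D bases the sample size on feasibility and says that inferential analyses are not central to the design. Section VIII.C expects 20% attrition and continues assessments in participants who do not comply with treatment.

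**The concern.** In a pilot that is meant to deliver an effect size, the width of the confidence interval is the main measure of what the exploratory analysis yields. A change score fixes the weight on the baseline value at exactly one. ANCOVA estimates that weight from the data. If the slope of week 20 on baseline is below one, as it is whenever baseline and follow-up are imperfectly correlated with similar SDs, subtracting the whole baseline adds noise that adjustment would remove. The baseline values are collected anyway, so any loss is avoidable. What is at stake is the width of an exploratory interval. The primary feasibility and acceptability aims are not affected.

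**Working it through.** The plan gives no precision or power figure for 3a/3b, so there is none to reproduce.

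**Inputs from the documents.** Phase II N is 60 in sections IV.A and IV.B but 40 in section II. Allocation is 1:1 (IV.A.ii) and attrition 20% (VIII.C). Completers are therefore 60 × 0.8 = 48 (24 per arm) or 40 × 0.8 = 32 (16 per arm).

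**Assumed inputs.** rho = 0.5, 0.7, 0.9, and k = week-20 SD / baseline SD = 0.8 to 1.25. The documents give neither.

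**Formula.** In units of the baseline variance, a change score has variance 1 + k² − 2·rho·k, and the ANCOVA residual has variance k²(1 − rho²). Estimating the slope costs a factor (N − 3)/(N − 4), which is 45/44 = 1.023 at N = 48 and 29/28 = 1.036 at N = 32. So

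ratio = k²(1 − rho²) / (1 + k² − 2·rho·k) × (N − 3)/(N − 4).

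Example at k = 1, rho = 0.5, N = 48: 0.75 / 1.00 × 1.023 = 0.767.

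**ANCOVA variance / change-score variance, 24 per arm**

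| k | rho 0.5 | rho 0.7 | rho 0.9 |
|---|---|---|---|
| 0.8 | 0.58 | 0.64 | 0.62 |
| 1.0 | 0.77 | 0.87 | 0.97 |
| 1.1 | 0.84 | 0.94 | 1.02 |
| 1.25 | 0.91 | 1.00 | 0.97 |

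With 16 per arm and k = 1 the ratios are 0.78, 0.88 and 0.98. The worst case in the range is about 1.035. A simulation at N = 48 and k = 1 gave 0.76, 0.89 and 0.98, in line with the formula.

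**Interval half-widths at k = 1, in baseline SDs (t-based)**

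| | rho 0.5 | rho 0.7 | rho 0.9 |
|---|---|---|---|
| 24 per arm, change | 0.581 | 0.450 | 0.260 |
| 24 per arm, ANCOVA | 0.509 | 0.420 | 0.256 |
| 16 per arm, change | 0.722 | 0.559 | 0.323 |
| 16 per arm, ANCOVA | 0.637 | 0.526 | 0.321 |

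**Where the gain vanishes.** The slope of week 20 on baseline is rho × k. When it is near 1, the change score already uses the right weight, and ANCOVA pays only for the extra parameter, about 2% to 4% of variance. Example: k = 1.1, rho = 0.9, slope 0.99, ratio 1.02 with 24 per arm.

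**Would week-10 values add much?** Section IV.B says "a fasting blood draw will be conducted at Week 0, Week 10, and Week 20", and Table 1 has a mid-treatment visit. With monotone dropout, the further variance ratio from using week 10 is (1 − r²) + r²·m/n₁. Here r is the week-10/week-20 correlation given baseline, m = 48 completers, and n₁ the number with week-10 data. At r = 0.5 and half of the 12 dropouts seen at week 10: 0.75 + 0.25 × 48/54 = 0.972. Over r from 0.3 to 0.7, with 25% to 75% of dropouts seen at week 10, the further reduction is 0.5% to 8%.

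**Standardiser.** At k = 1 the SD of change is √(2(1 − rho)) baseline SDs. A true difference of 0.50 baseline SD, divided by the SD of change, is reported as 0.50, 0.65 or 1.12 at rho 0.5, 0.7 or 0.9.

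**The case against.** The strongest reply is that this is a preference between two valid methods. Aim 3 is exploratory, the sample size is not set for inference, and the plan already leads with effect sizes and intervals, with Mann-Whitney tests in support. That stands, and it is why the point is minor.

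A second reply is that the gain rests on two unknown quantities. Equal SDs cannot be assumed: entry requires current illness (CGI-BP of 3 or more, section IV.B), which may narrow the baseline spread of symptom scores and push k above 1. That stands too. The k = 1 figures are one slice of a range that includes no gain and a slight loss.

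Third, the outcome named in the Phase II purpose may gain least. FRS is "based on six indices: age, gender, total cholesterol, HDL cholesterol", together with smoking, systolic blood pressure and blood-pressure medication. Several of these are fixed or slow to change, so rho may be high. At rho 0.9 and k = 1 the half-width barely moves (0.260 to 0.256). The case is better for MADRS, YMRS and LIFE-RIFT if their rho is moderate.

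None of this removes the point. In the range examined, the possible loss is about 2% to 4% of variance, and the possible gain is much larger.

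**Conclusion.** The point holds as a minor precision improvement. The 3a/3b comparison names no baseline covariate, and adjusting for baseline would probably narrow the interval. With 24 per arm, the variance falls by about 42% at best (k = 0.8, rho 0.5), by 23%, 13% or 3% at k = 1, and rises by about 2% at worst. With 16 per arm the worst case is a rise of about 3.5%. All of this rests on assumed values of rho and k.

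Three stronger readings are tempting, and the documents do not support them.

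- *The change-score comparison is wrong or biased.* It is not: under randomisation it is unbiased.
- *The plan must use week 10, which would deal with attrition.* The further gain is modest and depends on the assumed correlations. Nor does a repeated-measures model cure dropout bias. In simulations with 30 per arm, 20% lost and loss in one arm following worsening after week 10, its estimate was 0.02 to 0.04 SD further from the truth than completer change scores. Section VI.B.iii does not limit withdrawal for deterioration to the period before week 10.
- *The analysis time is undefined.* Section VIII.B.iii does not repeat it, but the hypotheses that it analyses set 20 weeks.

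**What to change.** In section VIII.B.iii, make the main 3a/3b estimate for each measure the week-20 between-group difference adjusted for the baseline value of that measure (ANCOVA), with 95% CI. Include all randomised participants with a week-20 value, and report by arm how many have none. Keep the Mann-Whitney test on change from baseline as a sensitivity analysis. In the same edit, name the standardiser of the effect size, for example the pooled baseline SD; this is a clarification.

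A repeated-measures model that adds week 10 may be listed as an optional sensitivity analysis, not as a remedy for dropout. For FRS it needs smoking status recorded after week 0. Section IV.C.x says "The Medical History form will collect the patient data necessary to calculate the FRS score", and Table 1 marks that form at week 0 only. Any FRS change score or week-20 FRS needs the same item, so the plan should show where it is recorded.

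The cost is a few lines of SAP text and a short model, with no new visits or measurements. The downside is a parametric model in a small sample, with no gain or a slight loss of precision if rho × k is near 1. The Phase II sample size (40 or 60) should be reconciled, because every interval width above depends on it.
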